### 8.4. Responsibilities

At the 28 week follow-up visit the clinical researcher conducting the visit will ask if the patient participant has had a reportable SAE. Members of the research team at the site will also record all reportable SAE events into the EDC system before the 28 week follow-up time-point.

The principal investigator (PI) at site, or their authorised delegate, is responsible for assigning the severity and causality of an event, recording the SAEs as detailed in Section 8.3 of this protocol, and entering the data into the EDC system. The EDC will be set up with a role-restricted task to allow only the PI or delegate to sign off the reportable SAEs within the system.

The chief investigator (CI) or authorised delegate SAEs on a monthly basis and confirm their agreement or disagreement with the PIs judgement on causality. The CI will only upgrade, not downgrade, any decision made by the site PI. Disagreements will be discussed with the Sponsor, CI and PI and the Sponsor will be responsible for a final decision.

The TSC will review SAE data to identify if there are any patterns of events and to identify safety issues.

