#### 7.7. Follow up Assessments

The clinical researcher will carry out a second visit to repeat most of the outcome measures completed at baseline with the PWD and their informal carer (see Table 2). For those in the intervention arm, this will take place 26 weeks after the start of the intervention. For those in the control arm, this will take place 28 weeks from baseline. The HUQ will also be completed at three months follow up by phone call. A fidelity checklist will be used to measure intervention fidelity.

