Baseline data collected (see Table 2)	Х				
2 Assessment visits by Intervention team including Timed Up and Go Test		X			
Up to 22 visits by Intervention team			X		
Final visits will include Goal attainment scaling and Timed Up and Go test					
Completion of diary		X	X		
Completion of HUQ	X			X	X
Informed consent of professionals and participants and observation of interventions received		X	X		
Informed consent and qualitative interview with some professionals regarding views on intervention.			X		
Qualitative interview with patients, informal carers and professionals views on intervention (subset of participants who consent to qualitative study)			X		
Follow up outcome data collected					Х

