#### 8. Maintain Intervention

### 8.1. Description of the Intervention

The Maintain intervention is a multidisciplinary complex intervention which is delivered in the patient participant's home. The intervention will be personalised to each participant, taking into account their physical abilities, their preference for activities and goals agreed by the therapist, the patient participant and their unpaid carer. The number of sessions the participant receives will also be tailored to their needs. The first two sessions will be assessment sessions which will be followed by up to 19 therapy sessions delivered over 12 weeks and booster sessions at 16 weeks, 20 weeks and 24 weeks. An intervention manual will detail the assessment and therapy procedures for the professionals.

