### Serious adverse events (SAE)

All deaths (from any cause) and hospitalisations due to falls, fractures or musculoskeletal injury will be recorded. Other SAEs will not be recorded or reported. Only related SAEs will be subject to expedited reporting.

Causality of reportable SAEs will be assessed by the site PI (or authorised delegate). All SAEs which are possibly, probably or definitely related to the intervention will be categorised as 'related'. If the PI or delegate is unable to assign causality within 24 hours of the site becoming aware of the event, the SAE will be treated cautiously and subjected to expedited reporting.

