# 10. Data management

#### 10.1. Data collection tools and source document identification

Data will be handled, computerised and stored in accordance with the Data Protection Act 2018. Patients' will be given a copy of their signed consent form to keep, a copy will be filed in the patients' medical notes and a copy will be filed in the investigator site file. A scanned copy will be uploaded to the secure online EDC system by site staff, in which only authorised members of the trial team will be able to access. The consent forms will be checked by an authorised member of the trial team and then deleted after the check is complete.

Paper case report forms (CRFs) designed by Exeter Clinical Trials Unit will be used to collect data which will then be input into a secure online study EDC system. CRFs will capture the date of completion and name of the person completing the CRF. The EDC system will mirror the paper CRFs and will be able to audit the users entering data, amending data and any other data changes. The eCRFs will be validated to query discrepancies in the data as well as querying missing data. SAE data will be the only exception to this method and will be entered into the EDC system directly (medical records will be used for source data). Audio recordings from qualitative interviews will be transcribed and the transcriptions will be saved as source data.

When data are captured on a CRF as the first recording of the data (e.g. participant reported outcome measures), the CRFs are the source data. Where data are accessed from medical records, the medical records will be the source data. Data on standardised outcome measures will be collected on the CRFs by clinical researchers. Data for the health economics component (HUQ) will be integrated into the CRFs. CRFs will be pseudonymised to protect the identity of the participants. Paper CRFs completed at the 6-month visits in participants' homes will be transferred to the participating site by the research nurse (or equivalent) where the data will be transcribed into the EDC system. Paper intervention CRFs will be stored securely at the relevant Trust premises and posted to Exeter CTU at the end of the intervention period. Data will then be entered into the EDC by an authorised member of the research team. Diaries will be returned to the research team at the end of the intervention. Data from the diaries will also be entered on to the EDC system.

Page 48 of 59

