### 5.6. Harms

All harms that have been collected shall be reported as a total number that have occurred in the duration of the trial, and then reported by group on an as-treated basis.

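### Detection of reportable SAEs may differ between arms: one scheduled enquiry at week 28, no stated method for finding events earlier or in people not seen, and far more staff contact in the intervention arm

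*Protocol*

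**What the plan says.** The set of reportable events is narrow. Protocol 8.3 states: "All deaths (from any cause) and hospitalisations due to falls, fractures or musculoskeletal injury will be recorded". Non-serious events and other SAEs are not recorded.

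Section 8.4 gives two routes to these events. The first is a direct question: "At the 28 week follow-up visit the clinical researcher conducting the visit will ask if the patient participant has had a reportable SAE". The second follows immediately: "Members of the research team at the site will also record all reportable SAE events into the EDC system before the 28 week follow-up time-point". Section 10.1 makes medical records the source data for SAEs. No section says what prompts the second route, how often it is carried out, or what check is made on participants who are not seen at week 28.

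Planned contact with staff differs by arm. For the intervention arm, section 8.1 states: "The first two sessions will be assessment sessions which will be followed by up to 19 therapy sessions delivered over 12 weeks". Boosters follow at weeks 16, 20 and 24. Table 3 shows two assessment visits in week 1 and then, for weeks 2 to 28, "Up to 22 visits by Intervention team". For both arms, section 7.7 adds: "The HUQ will also be completed at three months follow up by phone call". Both arms also keep a falls diary (7.8). Neither the diary nor the HUQ is linked to SAE recording.

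SAP 5.6 states: "All harms that have been collected shall be reported as a total number that have occurred in the duration of the trial". It then splits the counts by group, as treated. Under Protocol 8.3 and 8.4 the same data go to the Trial Management Group every 3 months and to the Trial Steering Committee every 6 months, and the committee reviews them for patterns and safety issues.

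**The concern.** A count of events by arm can be compared only if an event has a similar chance of being found in each arm. Here the one enquiry that is scheduled, and is the same in both arms, comes at the end and reaches only those who are seen. Before then the intervention arm has many more occasions on which a death or admission could come to light. Each visit has a structured proforma (8.1.3), and support workers complete a session CRF that captures problems preventing delivery (12.5). A death or an admission would be such a problem. Controls have no counterpart to these records.

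People who miss the final visit are also a selected group. Section 7.10 expects some participants to become ill or die before completion, and deaths and fall-related admissions are the reportable events.

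At stake is the reading of the only events the trial records as SAEs. An apparent excess in the intervention arm could come from better detection, and missed control events could hide in the same table. Until a participant reaches week 28, what the steering committee sees depends wholly on the route with no stated method. A full trial would probably inherit the procedure tested here.

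**Working it through.** **1. Contacts.** Protocol 8.1.3 gives a maximum of 22 sessions including boosters. This reproduces: 19 + 3 = 22. Adding the 2 assessment visits gives 22 + 2 = 24 intervention-team visits, of which 22 are therapy or booster sessions. All are maxima, because sessions are tailored. Controls have 1 scheduled staff contact between baseline and the final visit.

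**2. People who do not get the scheduled question.** Number = 60 × (1 − follow-up).
- Assumed follow-up of 80% (Protocol 9.1): 60 × 0.20 = 12.
- Go threshold of 70% (Protocol 4.4): 60 × 0.30 = 18.
- Across the protocol's 95% interval for follow-up, 66% to 91%: 60 × 0.34 = 20.4 down to 60 × 0.09 = 5.4.

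**3. Illustration of size.** The documents give no SAE rate and no detection rate, so everything in this step except the 30 per arm and the follow-up range is an assumption.
- True risk R is the same in both arms. It cancels from the ratio; 20% (6 of 30) is used for the counts.
- Control follow-up f is 0.7 to 0.8. Lost controls have k = 1 to 3 times the risk of retained ones. Every event in a retained control is reported at week 28.
- Control detection before any other capture: d_C = f / (f + (1 − f)k). Lowest: 0.7 / (0.7 + 0.3 × 3) = 0.4375. Highest: 0.8 / (0.8 + 0.2 × 1) = 0.80.
- Intervention detection d_I is 0.90 to 0.95.
- Site or records capture s finds the same share of otherwise missed events in both arms. Detection becomes D = 1 − (1 − s)(1 − d), and the apparent ratio is D_I / D_C.

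| s | Smallest ratio | Largest ratio |
|---|---|---|
| 0% | 0.90 / 0.80 = 1.125 | 0.95 / 0.4375 = 2.17 |
| 50% | 0.95 / 0.90 = 1.06 | 0.975 / 0.71875 = 1.36 |
| 90% | 0.99 / 0.98 = 1.01 | 0.995 / 0.94375 = 1.05 |

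In counts at s = 0 and R = 20%, controls show 6 × 0.4375 = 2.6 to 6 × 0.80 = 4.8 events and the intervention arm 6 × 0.90 = 5.4 to 6 × 0.95 = 5.7, against 6 true events in each arm.

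**4. A second set of assumptions.** Take 80% follow-up and 80% recall at week 28, so d_C = 0.8 × 0.8 = 0.64. Let team visits find 50% to 90% of what would otherwise be missed, so d_I = 1 − 0.36 × 0.5 = 0.82 to 1 − 0.36 × 0.1 = 0.964. The ratio is then 1.28 to 1.51 at s = 0%, 1.11 to 1.20 at 50%, 1.02 to 1.03 at 90%, and 1.00 when capture is complete.

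Both models show the same dependence. The answer turns on s, which the documents do not specify.

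**The case against.** The strongest reply is that the protocol already requires ongoing capture. Site teams in both arms must record all reportable SAEs before week 28, from medical records. Deaths and admissions for falls, fractures or musculoskeletal injury usually leave a record. The carer is an enrolled participant and may still be able to report a death. Withdrawal reasons are sought (Protocol 7.10), and losses are reported with reasons (SAP 4.3). The falls diary and the HUQ give similar information in both arms. No section makes a therapy visit an SAE collection point, and only three boosters follow week 12. Safety is stated not to be an outcome measure (8.3), no progression criterion uses SAEs (4.4), and SAP 5.6 specifies no model or test.

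Much of this stands. A reader might infer that the by-arm harms comparison rests on unequal ascertainment, or that events in people lost to follow-up are never found. The documents do not support either reading: not being asked at week 28 is not the same as not being ascertained, and detection through therapy visits is a possibility rather than a stated procedure.

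The reply does not close the gap. A duty to record an event does not say how the team learns of it. Naming medical records as source data says where a known event is documented; it does not schedule a search for each participant. The diary and HUQ could help, but neither feeds SAE recording, and diaries come back only at the end of the intervention (10.1).

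**Conclusion.** The point holds as a gap in method: differential detection of reportable SAEs between arms cannot be excluded, and nothing in the plan would show whether it had occurred. It is not shown that detection is unequal.

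Under equal true risk and the detection rates assumed in the first model, the apparent intervention-to-control ratio runs from 1.1 to 2.2 with no other capture, 1.06 to 1.36 with 50% capture of otherwise missed events, and 1.01 to 1.05 with 90%. A reader might take 2.2 as the expected distortion. It is the extreme of a case in which sites and records find nothing that the week-28 question misses in controls, which sits badly with the recording duty in 8.4. If records capture is nearly complete, the problem almost vanishes.

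The affected output is a descriptive count in a 60-person pilot, so this does not threaten the feasibility conclusions. It is worth changing because the remedy is cheap and the steering committee would learn of events earlier. The protocol read here is version 3.0, while SAP section 6 cites version 5.0, so first check that 8.4 has not since been revised.

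**What to change.** 1. In Protocol 8.4 and Table 3, add the reportable-SAE question to the 3-month HUQ call in both arms.
2. At week 28, check vital status and medical records for deaths and the listed admissions for every consented participant, including those not seen, within the terms of any withdrawal.
3. In SAP 5.6, base the by-group counts on these sources, which are the same in both arms, and list separately any event known only through an intervention visit.

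The second step does most of the work: it raises s in both arms, which moves the apparent ratio towards 1. The SAP was finalised during follow-up, so some 3-month calls may already have taken place. Steps 2 and 3 are still open for those participants.

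The cost is one question on an existing call, a records check for 60 people using a source the protocol already names, and a short addition to the SAP. The downside is a few minutes of staff time per participant.

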#### 8.5. Notifications of deaths

Deaths will be recorded in the EDC system with the cause of death recorded. RUSAEs will be reported to the TSC and the REC within 7 days of the Sponsor being made aware of the event.

### 8.6. Pregnancy reporting

Pregnancy is considered very unlikely, but if a participant becomes pregnant during their participation in the trial it will not be recorded or reported.

#### 8.7. Urgent safety measures

In the event of an immediate risk to participant safety, the Sponsor, CI, PI and/or TSC will make a decision to implement an urgent safety measure (USM).

PIs will implement USMs at sites and must be notified to the CI within 24 hours. The CI must notify the Sponsor within 24 hours of being made aware of an USM.

Page 44 of 59

If the CI and the Sponsor consider the USM to affect all participants, all PIs must be informed of the USM.

A protocol amendment must be submitted to the HRA and REC within three days following implementation of the USM. If the USM requires a temporary halt to the study, this will be notified by an amendment.

### 8.8. Annual report to the REC

An annual report will be submitted to the NHS REC who issued the favourable opinion using the appropriate form provided by the Health Research Authority.

# 9. Statistics and data analysis

### 9.1. Sample size calculation

We will randomise six rehabilitation services (clusters), one in each of 6 sites, and aim to recruit 60 PWD altogether (3 services and 30 PWD to each of the intervention and the control arms). Each service will recruit 10 PWD during the 6-month recruitment period, based on a recruitment rate of 1.7 PWD per service per month as achieved during our feasibility study. If recruitment is slower than expected, we will consider adding 2 additional sites.

The sample size calculation was based on the precision for estimating the proportion of eligible people that consent to participate in the study. We anticipate that we will have to approach 150 eligible people and 40% (60 participants) of these will agree to take part. The 150 who are screened is a large enough number to estimate the percentage that consent with a 95% confidence interval 29% to 51%. If the percentage that is followed up is 80%, 60 recruited participants is large enough to estimate this with a 95% confidence interval 66% to 91%, and the 30 participants in the intervention arm is large enough to estimate the percentage that attends at least 60% of the allocated sessions with a 95% confidence interval 60% to 93%. These confidence intervals take clustering into account [16] and are based on an assumed intra-cluster (intra-service) correlation coefficient of 0.05 to quantify variability across clusters in the feasibility parameters (i.e., percentage consented, followed-up, attending at least 60% of sessions).

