### Definite Stop ('red light'):

- < 10% of eligible participants consenting to pilot trial

- < 30% participants attend ≥ 60% of sessions as planned in a given intervention arm
- retention of < 50% of consented participants for provision of key outcome data at 6 months
- It is clear from the process data from participants and professionals that the intervention procedures have low fidelity in terms of content, frequency, duration and quality and/or that the intervention is not feasible to deliver.

Intermediate targets will be defined as amber and refinement of the study will be undertaken in conjunction with our PPIE panel and other key stakeholders. A decision as to whether to progress to planning a full trial will be discussed by the Trial Steering Committee.

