## **2.3. Sample Size**

We will randomise six rehabilitation services (clusters), one in each of 6 sites, and aim to recruit 60 PWD altogether (3 services and 30 PWD to each of the intervention and the control arms). Each service will recruit 10 PWD during the 6-month recruitment period, based on a recruitment rate of 1.7 PWD per service per month as achieved during our feasibility study. If recruitment is slower than expected, we will consider adding 2 additional sites.

The sample size calculation was based on the precision for estimating the proportion of eligible people that consent to participate in the study. We anticipate that we will have to approach 150 eligible people and 40% (60 participants) of these will agree to take part. The 150 who are screened is a large enough number to estimate the percentage that consent with a 95% confidence interval 29% to 51%. If the percentage that is followed up is 80%, 60 recruited participants is large enough to estimate this with a 95% confidence interval 66% to 91%, and the 30 participants in the intervention arm is large enough to estimate the percentage that attends at least 60% of the allocated sessions with a 95% confidence interval 60% to 93%. These confidence intervals take clustering into account [3] and are based on an assumed intra-cluster (intra-service) correlation coefficient of 0.05 to quantify variability across clusters in the feasibility parameters (i.e., percentage consented, followed-up, attending at least 60% of sessions).

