## 5.2. Analysis Methods

Participant flow through the trial will be summarised using a CONSORT flow diagram for cluster randomised controlled trials.

Baseline characteristics of the services and participants will be described using means and standard deviations for continuous and count variables and numbers and percentages for categorical variables. We will report the following parameters with 95% confidence intervals that are widened to allow for clustering: % of screened people that are eligible; % of eligible people that consent to participate; % of participants that provide data at the 6-month follow-up; and % of intervention arm participants that attend at least 60% of scheduled sessions. To estimate these parameters, mixed logistic regression models with Satterthwaite's degrees of freedom correction will be fitted to binary outcomes that represent eligibility status, consent status, follow-up status and whether attended at least 60% of the scheduled sessions. The constant from these models is the log odds of the parameters which will (along with the 95% CIs) be converted to the percentage scale.

We will also report estimates of the standard deviations for continuous outcomes measured at baseline and week 28.

In order to assess the extent to which randomisation of clusters before recruiting participants may have resulted in recruitment bias due to the research nurses being unblinded, we will report the percentage of eligible people that participate in each of the intervention and control arms and examine the characteristics of the participants between the trial arms.

Finally, in ancillary analyses, we will report intention-to-treat estimates of the effect of the intervention at week 28, using 95% confidence intervals to quantify potential effectiveness. The comparison between trial arms will be undertaken by fitting mixed ("multilevel") linear regression models for continuous outcomes and mixed Poisson regression models for count outcomes; in both instances, using Satterthwaite's degrees of freedom correction to recognise the small number of clusters in the study. Comparisons will be adjusted for the baseline score of the outcome. No p-values will be reported as it is not an objective of this study to conduct a definitive test of the intervention effect.

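### The stated 95% intervals appear to omit the small-cluster degrees-of-freedom correction that the analysis specifies; attendance, estimated from 3 clusters, may be far less precise than 60% to 93%

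*Protocol*

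**What the plan says.** Protocol 9.1 and SAP 2.3 give the same three precision statements.

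- Consent, assumed 40%: "The 150 who are screened is a large enough number to estimate the percentage that consent with a 95% confidence interval 29% to 51" per cent.
- Retention: "If the percentage that is followed up is 80%, 60 recruited participants is large enough" for an interval of 66% to 91%.
- Attendance: 30 intervention participants are said to be enough "to estimate the percentage that attends at least 60% of the allocated sessions with a 95% confidence interval 60% to 93" per cent.

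The inputs are "3 services and 30 PWD to each of the intervention and the control arms", with "Each service will recruit 10 PWD during the 6-month recruitment period". The intervals are said to allow for clustering and to be "based on an assumed intra-cluster (intra-service) correlation coefficient of 0.05". The source cited for the clustering method is [16] in the protocol and [3] in the SAP. No degrees-of-freedom correction is mentioned in either section.

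The analysis sections, protocol 9.2 and SAP 5.2, estimate the same percentages differently. Mixed logistic models with Satterthwaite's "degrees of freedom correction will be fitted to binary outcomes that represent eligibility status, consent status, follow-up status" and session attendance. The constant and its interval are then converted from log odds to a percentage. Attendance uses intervention-arm participants only, hence 3 clusters.

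Attendance is also a progression criterion (protocol 4.4). It is green when at least 80% of participants attend at least 60% of sessions, and red when "< 30% participants attend ≥ 60% of sessions as planned in a given intervention arm".

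**The concern.** A design effect shrinks the sample to an effective number of independent people, but it treats the intra-cluster correlation as known. The planned model estimates the between-cluster variance from 6 services for consent and retention, and from 3 for attendance. A Satterthwaite correction exists to pay for that uncertainty. For an intercept with k balanced clusters and a positive variance estimate, the df are about k−1. The multiplier is then 2.57 with 6 clusters and 4.30 with 3, against 1.96.

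If the planning intervals leave this out, the precision that justifies the sample size is better than the planned analysis can be expected to deliver. The gap is largest for attendance, where the steering committee would expect an interval about 33 points wide (93 − 60) and could see one much wider.

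The citation compounds the problem. In both reference lists the paper cited for clustering is the one on developing the DAD, and the protocol cites it under the same number for the DAD in Table 2. A reader cannot find out how the intervals were obtained.

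**Working it through.** **Inputs (protocol 9.1, SAP 2.3).** Consent: p = 0.40, n = 150, k = 6, so m = 150/6 = 25. Retention: p = 0.80, n = 60, k = 6, m = 10. Attendance: n = 30, k = 3, m = 10; p = 0.80 is carried over from the retention clause of the same sentence, because no separate value is given. ICC = 0.05.

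**Step 1: design effect.** DE = 1 + (m − 1) × ICC and n_eff = n/DE.

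- Consent: 1 + 24 × 0.05 = 2.20; 150/2.20 = 68.2
- Retention: 1 + 9 × 0.05 = 1.45; 60/1.45 = 41.4
- Attendance: 1.45; 30/1.45 = 20.7

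**Step 2: reproduce the stated figures.** A Jeffreys interval takes the 2.5% and 97.5% points of Beta(n_eff·p + 0.5, n_eff·(1 − p) + 0.5), with no df correction.

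| | Stated | Jeffreys on n_eff |
|---|---|---|
| Consent | 29–51% | 29.0–51.8% |
| Retention | 66–91% | 66.0–89.9% |
| Attendance | 60–93% | 59.6–92.7% |

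All limits agree to about 1 point. Other intervals without a df correction are in the same region for attendance (Wilson 58.8–91.8%, arcsine 60.6–94.0%, exact 56.8–94.1%). No variant tried with 2 df comes near 60–93%; a Wilson-type interval, for example, gives 34.9–96.8%.

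**Step 3: same inputs on the log-odds scale, t on k−1 df.** Interval = logit(p) ± t × SE, with SE = 1/√(n_eff·p·(1 − p)), back-transformed.

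- Consent: SE 0.247, t(5) = 2.571; −0.405 ± 0.635 gives 26.1–55.7%
- Retention: SE 0.389, t(5) = 2.571; 1.386 ± 0.999 gives 59.6–91.6%
- Attendance: SE 0.550, t(2) = 4.303; 1.386 ± 2.365 gives 27.3–97.7%

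With 1.96 in place of t, the same formula gives 29.1–52.0%, 65.1–89.5% and 57.7–92.2%. The widening therefore comes from the multiplier and not from the change of scale.

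**Step 4: dependence on df and ICC, attendance only.** Satterthwaite df depend on the data. At ICC 0.05:

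| df | Interval |
|---|---|
| 2 | 27–98% |
| 4 | 47–95% |
| 10 | 54–93% |
| 29 | 57–93% |

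At 2 df, ICC 0.01 gives 34–97% and ICC 0.10 gives 21–98%.

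**Step 5: how often 2 df would apply.** With 3 clusters of 10, 80% attendance and ICC 0.05, simulated beta-binomial data give a zero or negative ANOVA between-cluster variance in about 44–45% of trials; a linear F approximation gives 47%. In those trials software may return larger df and a narrower interval.

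**Step 6: check with an estimated standard error.** In the same simulations, a t interval with 2 df computed from the three cluster percentages (percentage scale, not truncated at 100%) has a median width of about 57 points, against the stated 33. Among trials with exactly 24 of 30 attending, the median lower limit is about 55%, and 8–9% of lower limits fall below 30%.

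**The case against.** Four points can be made for the plan.

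First, the interval formula is not named, so the missing correction is inferred. No formula tried matches all six limits exactly, and for consent alone an unclustered Wald interval with t on 4 df also rounds to 29–51%. That stands as a limit on certainty. However, that alternative fails for the other two intervals, while the design-effect calculation fits all three to about 1 point. A design effect alone is also a common planning simplification, and the documents do say that clustering was allowed for. No sum is shown to be wrong; the fault is a mismatch between planning and analysis.

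Second, a reader might infer that 27–98% is the interval the trial will report. The documents do not support that. The figure joins a standard error from a fixed ICC to a multiplier meant for an estimated one, and it needs 2 df. In a little under half of simulated trials the variance estimate would not be positive, and with 24 of 30 attending the lower limit is usually well above 27% (Step 6). It is one end of a range.

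Third, a reader might go on to infer that the trial cannot separate stop from go on attendance. This does not hold either. Protocol 4.4 applies cut-offs to observed percentages. Nothing there turns on whether a confidence limit crosses a threshold, there is an amber zone, and the steering committee discusses progression. Red and green are 50 points apart. At ICC 0.05, if true attendance were 30%, at least 24 of 30 attending occurred in at most a handful of 400,000 simulated trials; if it were 80%, fewer than 9 of 30 did not occur. At ICC 0.20 each probability stays below 0.1%.

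Fourth, the plan ties the calculation mainly to consent, which has 6 clusters, and the 10 per service also rests on the feasibility study's recruitment rate. That is right, and the 6-cluster changes are modest.

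**Conclusion.** The point holds as a mismatch between the planning precision and the planned analysis. The three intervals are matched by a method without the df correction that protocol 9.2 and SAP 5.2 specify. On 5 df, consent widens from 29–51% to about 26–56%, and the lower limit for retention falls from 66% to about 60%. These two figures assume ICC 0.05, balanced clusters and df of k−1.

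For attendance the stated 60–93% is optimistic by an amount that cannot be fixed in advance. The interval could run from about 27–98% at 2 df to close to the stated one if the between-cluster variance is estimated as zero and the software then uses large df. This also assumes the implied 80%.

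The citation error is certain and does not depend on any of these assumptions. The pilot's validity and its progression rules are not called into question. What needs correcting is the precision claimed for them.

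**What to change.** In protocol 9.1 and SAP 2.3:

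- Name the interval method and the df assumption, and restate consent as about 26–56% and retention as about 60–92% (log-odds scale, 5 df, ICC 0.05).
- State the 80% assumed for attendance. Give its precision as a range with the conditions attached: about 27–98% at 2 df, 47–95% at 4 df, and nearer 57–93% if the variance is estimated as zero and large df are used.
- Say that attendance precision from 3 clusters may be much lower than 60–93%, so its interval should be read descriptively.
- Replace the clustering citation ([16] in the protocol, [3] in the SAP) with a source for the method actually used.

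The cost is text only, plus a less favourable precision statement. No extra participants are needed, and neither the analysis model nor the progression criteria need change.
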